4.5 Pragmatic Trial

To determine mPATH-CRC’s effectiveness, we will nest a pragmatic trial within the implementation study. We will query the electronic health record (EHR) at each study clinic to identify unscreened individuals aged 50 – 74 who completed a clinic visit with a physician or advanced practice professional 4 to 12 months prior to the implementation launch date, and 0 to 8 months after the implementation kick-off launch date. Specific inclusion criteria are detailed in Section 3.0. We will then examine in the EHR whether these individuals complete CRC screening within 16 weeks of their index visit.

4.6 Mixed-Methods Study

The mixed-methods study will examine the facilitators and barriers to maintenance (sustained use of mPATH-CRC over time). In the 12th month after each clinic’s launch date, we will identify sites who have maintained use of the mPATH program throughout the study period. To supplement the quantitative data gathered with our clinic surveys (Section 4.4.6), we will conduct semi-structured interviews with four members of each clinic: the clinic champion, one clinician, one front desk team member, and one medical assistant/nursing team member. The clinic champion will assist in the identification of the other team members for interviews based on their experience with the mPATH program. All participants will receive a \$50 gift card. Using an interview guide (Appendix C), we will explore how mPATH-CRC was incorporated in the clinic’s work flow and factors that affected maintenance such as intervention adaptations, organizational characteristics, and the champion’s role. There will be a separate version of the interview guide for clinics who have very low (or no) usage of mPATH during their participation in the study.^{56,69,70} Members of clinics that opt to discontinue use of mPATH will be interviewed as soon as practical after they discontinue use. We will interview representatives from study clinics until thematic saturation is reached. These semi-structured interviews, expected to last approximately 30 minutes, will be conducted by phone or video conference and analyzed by staff trained in qualitative methods. Interviews will be audio recorded and transcribed verbatim. Transcripts will be imported into ATLAS.ti software,⁷¹ iteratively reviewed, coded by concept, and analyzed thematically to describe the implementation and sustainability experience. Themes will be compared among clinics to determine any differences.

5.0 Outcome Measures

5.1 Definition of Time Points

The Implementation Date will be defined as the date of the clinic launch at each site. A “month” is defined as a 4 week time period. “Week 1” commences the day of clinic launch.

EFFECTIVENESS AND IMPLEMENTATION OF MPATH-CRC: A MOBILE HEALTH SYSTEM FOR

COLORECTAL CANCER SCREENING

Wake Forest Baptist Comprehensive Cancer Center (WFBCCC)

WFBCCC # TBD

5.2 Primary Outcome

mPATH-CRC Reach: Proportion of all Spanish or English-speaking patients, ages 50 – 74, who are eligible for CRC screening and complete the mPATH-CRC program in the 6th month (weeks 21 – 24) following the implementation date. Patients who use mPATH™-CheckIn and are told they are due for CRC screening but advised to discuss screening with their doctor due to detected risk factors are also counted as having used mPATH™-CRC.

5.3 Secondary Outcomes

- 5.3.1 mPATH™-CRC Reach (by month): The proportion of patients aged 50-74 who are eligible for CRC screening who complete mPATH™-CRC or have risk factors identified by mPATH™-CheckIn in months 1-5 following implementation
- 5.3.2 mPATH™-CRC Reach (by socioeconomic strata): The proportion of patients aged 50-74 who are eligible for CRC screening who complete mPATH™-CRC or have risk factors identified by mPATH™-CheckIn in months 1-6 by socioeconomic strata; this outcome will also be calculated among CheckIn users only
- 5.3.3 mPATH™-CRC Adoption: The mean usage of mPATH™-CRC among staff and providers over the first 6 months following implementation; usage is calculated for each staff/provider as the proportion of times mPATH™-CRC is completed out of the total times mPATH™-CRC should have been launched.
- 5.3.4 mPATH™-CRC Acceptability, Appropriateness, and Feasibility: Mean Acceptability of Intervention Measure (AIM), Intervention Appropriateness Measure (IAM), and Feasibility of Intervention Measure (FIM) scores (68) for mPATH™-CRC as assessed on the 6-month clinic personnel survey
- 5.3.5 mPATH™-CRC Implementation Fidelity: The proportion of patients who use mPATH™-CRC and request a CRC screening test who have a test ordered or have the order dismissed (i.e., “self-order” feature is used as designed) in months 1-6
- 5.3.6 mPATH™-CRC Maintenance: The proportion of patients aged 50-74 who are eligible for CRC screening who complete mPATH™-CRC or have risk factors identified by mPATH™-CheckIn in months 7-12
- 5.3.7 mPATH™-CheckIn Reach: The proportion of patients aged 18 or older who complete mPATH™-CheckIn in months 1-6; this outcome will be calculated overall and within socioeconomic strata
- 5.3.8 mPATH™-CheckIn Adoption: The mean usage of mPATH™-CheckIn among staff and providers over the first 6 months following implementation; usage is calculated for front desk staff as the proportion of times mPATH™-CheckIn is completed out of the total times mPATH™-CheckIn should have been handed out; usage is calculated for nurses/providers as the proportion of times mPATH™-CheckIn is completed and data is transmitted to the EHR out of the total times mPATH™-CheckIn should have been handed out
- 5.3.9 mPATH™-CheckIn Acceptability, Appropriateness, and Feasibility: Mean AIM, IAM, and FIM scores for mPATH™-CheckIn as assessed on the 6-month clinic personnel survey
- 5.3.10 mPATH™-CRC Maintenance: The proportion of patients aged 18 or older who complete mPATH™-CheckIn in months 7-12

EFFECTIVENESS AND IMPLEMENTATION OF MPATH-CRC: A MOBILE HEALTH SYSTEM FOR

COLORECTAL CANCER SCREENING

Wake Forest Baptist Comprehensive Cancer Center (WFBCCC)

WFBCCC # TBD

- 5.3.11 mPATH™-CRC Effectiveness: The proportion of patients aged 50-74 who are eligible for CRC screening who complete CRC screening within 16 weeks of their index visit to the clinic. Effectiveness is determined by comparing the proportion who complete screening in a pre-implementation cohort (months 12 - 4 before implementation) to a post-implementation cohort (months 1 - 8 after implementation).
- 5.3.12 CRC screening tests ordered: The outcome is defined as the proportion of patients aged 50-74 who are eligible for CRC screening who have a CRC screening test ordered (colonoscopy, flexible sigmoidoscopy, fecal testing for blood, or fecal DNA testing) within 16 weeks of their index visit to the clinic. This outcome will also be compared between the pre- and post-implementation cohorts.
- 5.3.13 Facilitators and barriers to maintenance (sustained use of mPATH™-CRC over time): These will be identified through semi-structured interviews. Interviews will explore how mPATH™-CRC was incorporated in the clinic's work flow and factors that affected maintenance such as intervention adaptations, organizational characteristics, and the champion's role. Interviews will be conducted with four members of each selected clinic: the clinic champion, one clinician, one front desk team member, and one medical assistant/nursing team member.

5.4 Exploratory Outcomes

- 5.4.1 mPATH™ Implementation Cost: Cost to implement and maintain usage of the mPATH™ program from the perspective of a healthcare system considering implementation, including hardware (i.e., iPads, cases, charging cabinets), cloud data storage fees, training, and technical support. Clinic staff training costs will be computed using training time and national average wage values for nursing and other staff from the Bureau of Labor Statistics. Technical support costs will include travel and support staff time costs associated with the initial training, and any follow-up trainings. Ongoing costs to maintain usage of mPATH™ include costs to train new employees or replace hardware and technical support costs related to follow-up training, troubleshooting, and adapting the program as needed

5.5 Data Sources

- 5.5.1 Electronic health record (EHR) and appointment schedules: Each clinic's EHR and appointment schedules can be queried to identify patients scheduled for visits, patients who completed visits, patient demographics, and patient clinical care data.

- 5.5.2 mPATH-CRC database: The mPATH program database includes patients' medical record numbers, age, gender, date/time of use, length of time in program, and responses to questions. (Appendix B)

- 5.5.3 REDCap Database: We will have a secure REDCap database that contains all clinic staff surveys and details on cost and contact with clinics.

6.0 Analytic Plan

6.1 Sample Size and Power

6.1.1 Primary outcome: Our primary objective is to assess differences in mPATH-CRC Reach proportion of participants who complete the mPATH-CRC program or have risk factors identified by mPATH-CheckIn) in the 6th month between the two implementation strategies. Using formulae found in Hemming et al.,⁷² **Table 3** shows the number of clinics necessary to detect differences in Reach ranging from .15 to .20 with 80% and 90% power for intraclass correlations (ICC) ranging from .03 to .08, assuming an average sample size per clinic of 30 with a cluster sample size coefficient of variation (CV) of 25%. These latter numbers are based on estimated numbers of eligible patients seen monthly, obtained from a

survey of the participating clinics. Since these data will be obtained from the EHR,

Table 3. Total number of clinics needed to detect the specified difference in Reach as a function of the power, ICC, and difference.

| Diff/ICC | 80% Power | | | | | | 90% Power | | | | | |
|----------|-----------|-----|-----|-----|-----|-----|-----------|-----|-----|-----|-----|-----|
| | .03 | .04 | .05 | .06 | .07 | .08 | .03 | .04 | .05 | .06 | .07 | .08 |
| .15 | 22 | 26 | 29 | 33 | 36 | 40 | 30 | 34 | 39 | 44 | 48 | 53 |
| .20 | 12 | 14 | 16 | 18 | 20 | 22 | 16 | 19 | 22 | 24 | 27 | 29 |

we will use all eligible patients at each site. We will recruit a total of 22 clinics, which will provide at least 80% power to detect a difference of 15% if the ICC is 0.03 or lower. If the ICC were as high as 0.08, we would have over 80% power to detect a difference of 20%. These calculations assume average utilization across all sites of 50%. Power increases as rates move away from 50% in either direction.

6.1.2 Effectiveness outcome: A secondary objective is to assess the effect of mPATH-CRC on screening rates (effectiveness) comparing 8 months of data prior to implementation to 8 months of data following implementation. The detectable difference (difference in screening rates pre vs post) depends on the sample size, power, ICC, and cluster sample size CV. We will assume a screening rate in the pre-implementation group of 15%, as observed in the control group in our R01 study.⁴⁵ Using SS/Power formulae for cluster designs^{72,73}, **Table 4** shows the differences in screening rates we will be able to detect

with 80% and 90% power for ICCs ranging from 0.03 to 0.06, assuming an average monthly sample size of 30 patients per clinic in the EHR, a cluster sample size CV of 25%, and no change in the screening trends over time. Because of the diminishing return of cluster designs, additional patients have little effect on the detectable difference, although we will use all the patients in the EHR. We see that we will be able to detect a 10% difference in screening rates (15% vs 25%) with 80% power even if the ICC is as large as 0.04. We estimate that a minimum of 30 patients per clinic per month will meet inclusion criteria for this analysis (based on age, language, and screening status) and will be available through the EHR, so we will be amply powered for assessing the secondary aim.

To evaluate whether the effect of mPATH-CRC on screening rates differs by implementation strategy, the period (pre vs post) by strategy (“high touch” vs “low touch”) interaction can be evaluated. Based on the control group from the previous randomized-controlled efficacy study, we anticipate a screening rate of 15% for “low touch” and pre- implementation. An increase in

Table 4. Detectable difference in screening rates as a function of the Power and the ICC (22 Clinics)

| ICC | 80% Power | | | | 90% Power | | | |
|-----|-----------|------|------|------|-----------|------|------|------|
| | .03 | .04 | .05 | .06 | .03 | .04 | .05 | .06 |
| | .087 | .100 | .113 | .125 | .102 | .118 | .133 | .146 |

EFFECTIVENESS AND IMPLEMENTATION OF MPATH-CRC: A MOBILE HEALTH SYSTEM FOR

COLORECTAL CANCER SCREENING

Wake Forest Baptist Comprehensive Cancer Center (WFBCCC)

WFBCCC # TBD

the screening rate from 15% to 25% from pre to post, corresponds to an odds ratio (OR) of 3.

Similarly, assuming a screening rate in the “low touch” group of 15%, and a screening rate of 25% in the “high touch” group, also corresponds to an OR of 3. By design, we anticipate half of the patients being in the “high touch” group and half in the post period, and that strategy and period are independent. Based

on these assumptions, **Table 5** shows the interaction OR that can be detected with 80% power for ICCs ranging from 0.03 to 0.06, assuming an average monthly sample size of 30 patients per clinic in the EHR (for 8 months pre and 8 months post), a cluster sample size CV of 25%, and no change in the screening trends over time.

Table 5. Detectable interaction odds ratio difference in screening rates as a function of the ICC (22 Clinics)

| ICC | 80% Power | | | |
|-----|-----------|-------|-------|-------|
| | .03 | .04 | .05 | .06 |
| | 2.903 | 3.462 | 4.097 | 4.819 |

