4.4.5. Implementation and Clinic Randomization

We will randomly implement mPATH-CRC in 2 clinics (1 “high touch” and 1 “low touch”) until all 22 clinics are enrolled. To control for major organizational differences that could impact implementation, we will first select 2 clinics of similar size, then randomly assign one to receive the “high touch” strategy and the other the “low touch” strategy.

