6.2 Analysis of Primary Outcome

We will assess the primary hypothesis (that the “high touch” vs. “low touch” implementation strategy will result in greater use of the intervention) using a mixed effects logistic regression model with mPATH-CRC Reach (Y/N) as the individual-level outcome, implementation approach as the primary independent variable, site as a random effect, and the stratification factor clinics size as a covariate per the design. A descriptive approach will also be utilized where mPATH-CRC Reach is estimated and reported along with an exact 95% confidence interval for each month (for months 1-6 following implementation), and within socioeconomic strata for “high touch” and “low touch” clinics separately. In secondary analyses, we will assess effects of clinic-level covariates (e.g. volume, rurality, organizational culture) and patient level covariates (e.g. age, gender, race/ethnicity) on Reach. We will include arm-by-covariate interactions to determine if the effect of the implementation strategy differs depending on levels of the covariates. This secondary analysis will allow us to determine effects of the implementation strategy in clinics with varying organizational factors and populations. The proposed approach allows us to incorporate participant- and cluster-level covariates, but there are other analysis methods we could employ. For example, we could use a clinic-level analysis (e.g. analysis of covariance) on the mean implementation rates within each clinic, or another individual-level approach (e.g. generalized estimating equations). Alternative methods and their strengths and weaknesses are well-documented.⁷⁴⁻⁷⁶ These alternate approaches will be used in a sensitivity analysis to determine effects of the modeling assumptions on the results.

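### The 80% power claimed for the primary Reach comparison rests on normal quantiles; with 22 clinics and a test that holds 5% error it is about 76%

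*Combined protocol and SAP*

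**What the plan says.** Section 6.1.1 fixes the size of the trial: "We will recruit a total of 22 clinics". The reason given for that number is its power at the lower end of the ICC range, in these words: "which will provide at least 80% power to detect a difference of 15% if the ICC is 0.03 or lower". The section then adds a claim for a larger difference: "If the ICC were as high as 0.08, we would have over 80% power to detect a difference of 20" percentage points.

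The inputs are given there too: "assuming an average sample size per clinic of 30 with a cluster sample size coefficient of variation (CV) of 25" per cent, and "These calculations assume average utilization across all sites of 50" per cent. The 80% power row of Table 3 for a 15-point difference reads "15 | 22 | 26 | 29 | 33 | 36 | 40" for ICC 0.03 to 0.08. The cell for 20 points at ICC 0.08 is also 22. The section does not state alpha, sidedness, the reference distribution or degrees of freedom.

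Under 4.4.5, clinics are allocated in twos: "we will first select 2 clinics of similar size, then randomly assign one to receive the" more intensive strategy and the other the less intensive one. That gives 11 clinics per arm.

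The primary analysis in 6.2 is a mixed effects logistic regression with "site as a random effect, and the stratification factor clinics size as a covariate per the design". No small-sample method is named. A clinic-level analysis appears only as a sensitivity analysis.

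**The concern.** Clinics are randomised, so the precision of the arm effect is estimated from the variation between 22 clinics, however many patients each contributes. That leaves 22 − 2 = 20 degrees of freedom, or 19 once clinic size is a covariate. Normal quantiles treat the between-clinic variance as known. With so few clinics this overstates power unless the test itself also ignores the uncertainty, in which case it rejects too often under the null.

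The printed figures have no slack to absorb the correction, since 22 is the smallest whole number that meets 80% by the normal method. These two sentences are the stated reason for 22 clinics. The unnamed reference distribution also affects the confirmatory p-value, not only the planning.

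**Working it through.** **Inputs** (6.1.1 unless noted): mean clinic size m = 30; CV = 0.25; average Reach 50%, so 42.5% vs 57.5% (d = 0.15) or 40% vs 60% (d = 0.20); k = 11 clinics per arm (4.4.5). Assumed: two-sided 5%, which fits the 95% intervals in 6.2 and reproduces Table 3. A one-sided 5% test would need about 17 clinics for the 15-point, ICC 0.03 cell.

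**Step 1. Reproduce the plan's figures with normal quantiles.**

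Design effect: DE = 1 + [(1 + CV²)m − 1] × ICC = 1 + 30.875 × ICC.
- ICC 0.03: DE = 1.926
- ICC 0.08: DE = 3.470

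Clinics in total = 2 × (1.960 + 0.842)² × (p₁q₁ + p₂q₂)/d² × DE/m.
- d = 0.15: p₁q₁ + p₂q₂ = 0.48875, so 170.5 per arm before clustering; 2 × 170.5 × 1.926/30 = **21.89**, printed 22
- d = 0.20: p₁q₁ + p₂q₂ = 0.48, so 94.2 per arm; 2 × 94.2 × 3.470/30 = **21.79**, printed 22

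The rest of the 15-point, 80% row comes to 25.40, 28.91, 32.42, 35.93 and 39.44, which round up to the printed 26, 29, 33, 36 and 40. Over the whole table, 18 of 24 cells match on rounding up and all are within one clinic.

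**Step 2. Power at 22 clinics.**

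SE = √[(p₁q₁ + p₂q₂) × DE/(m × k)] with m × k = 330, and λ = d/SE.

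| Claim | SE | λ | Normal, critical value 1.960 | t, 20 df, critical value 2.086 | t, 19 df |
|---|---|---|---|---|---|
| 15 points, ICC 0.03 | 0.0534 | 2.808 | 80.2% | **76.2%** | 75.9% |
| 20 points, ICC 0.08 | 0.0710 | 2.815 | 80.4% | **76.4%** | 76.1% |

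The t columns use the noncentral t distribution with the same λ. Other common choices (variance taken as p(1 − p) = 0.25, another cluster-size correction, or none) move the 20 df figures to between 75.2% and 77.4% for 15 points at ICC 0.03 and between 74.7% and 78.2% for 20 points at ICC 0.08.

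**Step 3. What 22 clinics do deliver at 80% power with t on 20 df.**
- Largest ICC: 0.024 for 15 points and 0.070 for 20 points
- Detectable difference: 15.7 points at ICC 0.03 and 20.9 points at ICC 0.08
- Clinics for 80%: 24 in both cells (12 per arm gives 80.0% and 80.2%)

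**Step 4. Type I error.** Using 1.960 where t on 20 df applies gives a true error of 6.4%. Beta-binomial simulation of an unweighted clinic-level comparison (11 vs 11 clinics, mean size 30, CV 0.25, 40,000 runs) agrees:

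| Setting | t: type I error | t: power | 1.96: type I error | 1.96: power |
|---|---|---|---|---|
| 15 points, ICC 0.03 | 5.0% | 75.5% | 6.4% | 79.1% |
| 20 points, ICC 0.08 | 5.2% | 76.4% | 6.6% | 80.0% |

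A random-intercept logistic model tested by Wald z, without the size covariate (3,000 runs), had type I error of about 7.6% at ICC 0.03 and 8.5% at ICC 0.08.

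**The case against.** Nothing is miscomputed: the plan applies a cited cluster-trial formula, and normal quantiles are that formula's convention. The use of z is itself inferred, and six Table 3 cells do not match on rounding up. This is fair as to how the figures arose. But the mismatches are at most one clinic, a t-based calculation gives 24 and not 22 in both cells, and a convention does not make the stated power true for 22 clinics.

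The 50% average is conservative, as 6.1.1 says. With t on 20 df, average Reach of 35% or 65% gives 80.0% and 80.3%, and 30% or 70% gives 83.2% and 83.5%. This stands as context, but both claims are made at 50%, and 76% should be reported with that condition attached.

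Matching on size and the size covariate may reduce variance. A 10% reduction, taken purely as an illustration, would restore 80.2% and 80.4% on 19 df. The documents give no figure for such a gain. If the pairs were analysed as pairs (10 df) with no gain from matching, power would be about 72%.

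The error inflation depends on a test that 6.2 leaves open. That is true, and it is the reason to name one. The simulated logistic model shows that inflation also arises with the planned type of model. The clinic-level sensitivity analysis does not settle it, because it is not the confirmatory test.

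Finally, ICC uncertainty matters more: Table 3 runs from 22 to 40 clinics in one row. This is correct, and it limits the weight of the point to a correction of wording.

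**Conclusion.** The concern holds. At the plan's own inputs, 22 clinics give about 76% power for both quoted scenarios under a test that holds 5% error, about 4 points below what is stated. The normal-method margin over 80% is only 0.2 and 0.4 points, so any reasonable small-sample correction takes both claims below 80%. The plan can have about 80% power or a 5% error rate at these settings, but not both.

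This rests on a two-sided 5% test, 11 clinics per arm, average Reach of 50%, no variance reduction from clinic size, and the inference that Table 3 was built with normal quantiles. For 15 points, 80% power remains true for ICCs up to about 0.024. The shortfall should be corrected in the text, but it does not undermine the design.

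**What to change.** 1. In 6.1.1, replace the two power statements with about 76%, on the stated condition of 50% average Reach. Alternatively keep 80% and give the detectable differences as about 15.7 points (ICC 0.03) and 20.9 points (ICC 0.08). State alpha and sidedness.
2. Recompute Table 3 with t quantiles, rounded up to whole pairs of clinics. The two cells that support the claims become 24.
3. In 6.2, state that the arm effect is tested with clinic-based degrees of freedom (between-within or Kenward-Roger type, about 19 to 20), or make the clinic-level t test the confirmatory analysis.

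The cost is a few sentences, one table and a stated power about 4 points lower. No clinics are added and no data collection changes.

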mPATH-CRC is our iPad-based application, designed for individuals with low literacy, which patients use during routine health care visits.³⁶ Because most Americans over age 50 have seen a doctor within the past year, including 75% of adults with less than a high school education, interventions in medical practices have a potential broad reach.³⁷ mPATH-CRC also sends automated text messages to help patients complete their screening tests, which extends support beyond the medical encounter. 95% of US adults own a cellphone, and there is no digital divide along racial or socioeconomic lines, which creates an opportunity to encourage healthy behaviors and potentially reduce health disparities.³⁸⁻⁴¹ Our mPATH-CRC intervention leverages the high prevalence of medical encounters and cellphone ownership to maximize its reach.

While several tests exist for CRC screening, most clinicians encourage colonoscopy, the most invasive and costly option.^{33,42} Because CRC screening rates are higher when patients can choose fecal occult blood testing, there is a critical need for interventions to help patients decide which test they prefer.^{11,43} Our mPATH-CRC program uses a validated decision aid to inform patients of the commonly used screening tests and help them select their best option,⁴⁴ a direct recommendation of the Cancer Moonshot Implementation Science Working Group Report.¹ In our previous randomized, controlled efficacy trial of 450 patients, mPATH-CRC more than doubled CRC screening rates (30% vs 15%, p=0.0001).⁴⁵ This efficacy trial demonstrated the potential for mPATH-CRC to improve screening rates,

EFFECTIVENESS AND IMPLEMENTATION OF MPATH-CRC: A MOBILE HEALTH SYSTEM FOR

COLORECTAL CANCER SCREENING

Wake Forest Baptist Comprehensive Cancer Center (WFBCCC)

WFBCCC # TBD

but the implementation was led by our research team, thereby restricting its potential for scale-up in a real-world context. This major gap is now addressed in this planned Type III hybrid implementation trial.

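### Section 6.1.2 does not show that the trial can detect a plausible high- versus low-touch difference in screening change, and the odds ratios behind Table 5 are wrong as written

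*Combined protocol and SAP*

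**What the plan says.** Section 2.2.2 defines the primary effectiveness analysis as the pre- versus post-implementation comparison of screening completion in high- versus low-touch clinics. Section 6.3 fits it as an interaction in a mixed logistic model.

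Section 6.1.2 first powers the overall pre/post comparison (Table 4) and ends that paragraph with "so we will be amply powered for assessing the secondary aim". A new paragraph turns to the period-by-strategy interaction. Its inputs are:

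- reference rate: "Based on the control group from the previous randomized-controlled efficacy study, we anticipate a screening rate of 15% for" low touch and pre-implementation
- period effect: "the screening rate from 15% to 25% from pre to post, corresponds to an odds ratio (OR) of 3"
- strategy effect: 15% in low touch "and a screening rate of 25% in the “high touch” group, also corresponds to an OR of 3"
- half the patients in each strategy and half in each period, 30 patients per clinic per month for 8 + 8 months, 22 clinics, cluster-size CV 25%

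Table 5 gives the detectable interaction OR at 80% power for ICCs of .03, .04, .05 and .06: "2.903 | 3.462 | 4.097 | 4.819". The section states no expected interaction to set against these values.

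Three figures elsewhere bear on what to expect. Section 6.1.1 powers Reach for differences of .15 to .20 and says "These calculations assume average utilization across all sites of 50" percent. Section 1.0 reports the efficacy trial as "30% vs 15%, p=0.0001". Section 4.4.2 gives low-touch clinics mPATH with the same kick-off training and materials as high-touch clinics.

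**The concern.** A detectable interaction OR of 2.9 or more is very large when both arms receive the same program and differ only in the support given to use it. Labelling 15% against 25% as an OR of 3 makes the section's own scenario appear to clear the smallest entry in Table 5. With the correct OR it does not.

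At stake is how a null result is read. If power for a realistic contrast is low, no significant difference is the likely outcome even when mPATH works and high touch raises use as hoped. Nothing in the plan guards against reading that as evidence that strategy does not affect screening.

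**Working it through.** **1. Reproduce Table 5.** Two-sided alpha 0.05 is assumed, because Section 6.1.2 does not state it. Total N = 30 × 16 × 22 = 10,560, or 2,640 per cell.

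Design effect = 1 + [(1 + CV²·21/22)·480 − 1]·ICC. At ICC .03 this is 1 + 507.6 × .03 = 16.23, so the effective N is 10,560/16.23 = 651, or 163 per cell.

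The detectable OR solves ln(OR) = (1.960 + 0.842) × √[Σ 1/(n·p·(1−p))] over the four cells.

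| Inputs | ICC .03 | .04 | .05 | .06 |
|---|---|---|---|---|
| Table 5 | 2.903 | 3.462 | 4.097 | 4.819 |
| Low-touch pre 15%, both main-effect ORs 3 | 2.901 | 3.463 | 4.095 | 4.823 |
| Both main-effect ORs 1.889 | 2.859 | 3.352 | 3.871 | 4.426 |
| Low touch flat (period OR 1), strategy OR 1.889 | 3.000 | 3.524 | 4.069 | 4.644 |
| Low touch flat (period OR 1), strategy OR 3 | 2.953 | 3.474 | 4.023 | 4.608 |

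Of the variants tried, only the first fits, to within 0.1%.

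**2. Cell rates that this implies.** The odds at 15% are .1765.
- Low-touch post and high-touch pre: .1765 × 3 = .529, or 34.6%.
- High-touch post: .1765 × 9 × 2.903 = 4.61, or 82% (ICC .03). With 4.819 it is 7.65, or 88% (ICC .06).

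Randomized arms would therefore differ before launch (15% against 34.6%). This conflicts with the 15% pre-implementation rate and with a post rate of 25%.

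**3. The stated ORs.** (.25/.75)/(.15/.85) = 1.889, not 3. If low touch stayed at 15% and high touch rose to 25%, the interaction OR would be 1.889. By the plan's method its power is 33% at ICC .03, falling to 19% at ICC .06. Full use against no use with the efficacy effect gives (.30/.70)/(.15/.85) = 2.43, also below 2.903.

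**4. An illustration from the plan's figures.** Post rate = 15% + 15 points × use, with 15% pre in both arms.
- Reach gap 15 points (57.5% vs 42.5% use): 23.6% vs 21.4%, OR 1.138.
- Reach gap 20 points (60% vs 40% use): 24.0% vs 21.0%, OR 1.188.

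**5. Power at 2,640 per cell.** Without clustering, SE = √[Σ 1/(2,640·p·(1−p))] ≈ 0.1015. For OR 1.138, 0.129/0.1015 = 1.27, power 25%. For OR 1.188, 0.172/0.1015 = 1.70, power 40%. The unclustered detectable OR is exp(2.802 × 0.1015) = 1.33.

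The plan's design effect treats all variation between clinics as noise, although the interaction is a within-clinic change. With m = 240 per clinic-period and between-period correlation c (assumed .8 to .9), the factor is 1 + (1.0625m − 1)·ICC − 1.0625m·ICC·c. It runs from 1.74 (ICC .03, c = .9) to 4.00 (ICC .06, c = .8).

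| Variance | OR 1.138 | OR 1.188 |
|---|---|---|
| Plan's design effect, ICC .03–.06 | 6% | 6–7% |
| Clinics as own controls, assumed ICC .03–.06, c = .8–.9 | 10–16% | 14–25% |
| No clustering | 25% | 40% |

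**6. More patients.** Section 3.3.2 expects at least 30,000 patients over 24 months. Taking 16/24 of them gives 20,000, or 5,000 per cell. If all fell in the two windows there would be 7,500 per cell. Unclustered power is then 42% and 65% at 5,000 (OR 1.138 and 1.188), and 57% and 82% at 7,500. With the assumed clustering it is at most about 36%.

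**The case against.** Several points on the other side have force.

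- The sentence promising ample power closes the overall pre/post paragraph. The plan makes no explicit adequacy claim for the interaction and prints its large detectable ORs openly. That stands. But the sentence refers to the secondary aim, and Section 2.2.2 makes high versus low that aim's primary analysis, so the scope needs stating.
- The 50% and the 15 to 20 points are power inputs for month-6 Reach, not forecasts. That stands, so 1.14 to 1.19 is an illustration. A wider gap changes the picture: 60% against 30% use (not a plan figure) gives 24.0% against 19.5%, OR 1.30, and unclustered power of 74%. With the factors 1.74 to 4.00 that falls to about 50% to 25%.
- Table 5 is probably too pessimistic, because it applies the full between-clinic design effect to a within-clinic change. That also stands. The 19% to 33% in step 3 depends on that method and would be much higher with clinics as their own controls. For ORs of 1.14 to 1.19, though, power stays low at 2,640 per cell even with clustering removed.

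A reader might infer that Table 5 holds low-touch clinics at 15% after launch, as if mPATH had no effect there. The loose wording permits this, but the calculation does not use it: flat low touch fails to reproduce the table, and the inputs that fit put low-touch post at 34.6%. For the same reason Table 5 does not encode a high-touch post rate of 34% to 46%, which is what its ORs would give from a flat 15%. Nor is 25% to 40% a ceiling on power, since the plan will use all EHR patients and their number may exceed 30 per clinic-month.

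**Conclusion.** Wrong as written. The OR of 3 should be 1.89, and Table 5 rests on cell rates that contradict the section's own scenario. Nothing in 6.1.2 shows that a plausible high- versus low-touch contrast is detectable. On the illustration the expected contrast is about 2.3 to 3.0 percentage points (OR 1.14 to 1.19), with power of 6% to 40% at the planned 2,640 per cell, depending on the variance.

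The illustration assumes an additive 15-point benefit in users only, with month-6 use applied to all 8 months. A 10-point benefit would give ORs of only 1.10 to 1.13. The between-period correlation is assumed, because the plan gives none.

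The weight is moderate. Reach is the primary outcome and effectiveness is secondary, so the trial's main inference is unaffected.

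**What to change.** In Section 6.1.2:

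1. Correct both OR-of-3 statements to 1.89.
2. State all four cell rates, with 15% pre-implementation in both arms and post rates scaled by Reach, labelled as assumptions.
3. Recompute Table 5 with a pre/post cluster variance that includes a between-period correlation, and state alpha.
4. Give the expected interaction and its power as a range over ICC, correlation and sample size, not as a ceiling.
5. Limit the ample-power sentence to the overall pre/post comparison, and tie it to Table 4. On the same illustration, 50% use × 15 points = 7.5 points, below Table 4's smallest detectable difference of 8.7.

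In Sections 2.2.2 and 6.3, say that the high- versus low-touch contrast will be reported as an estimated difference in change with a 95% CI, and that a non-significant result will not be taken as evidence of no difference.

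The cost is protocol and SAP wording, one recalculation, and a less favourable stated figure. No extra patients or clinics are needed.
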